7.5 SECONDARY ENDPOINTS

7.5.1 Key secondary endpoints

This section is not applicable as no key secondary endpoint has been specified in the protocol.

7.5.2 Other secondary endpoints

7.5.2.1 Phase Ib

This section is not applicable as no other secondary endpoint has been specified in the protocol.

7.5.2.2 Phase II

Secondary endpoints will be analysed descriptively for all patients in the randomised set in the second part of this trial. As for the primary analysis, only response assessments until the cut-off date of 25th November 2016 will be used for the analysis of all response-based endpoints.

Time-to-progression

TTP will be assessed based on the Kaplan-Meier method for each treatment arm separately. Point estimates together with CIs (based on Greenwood's method) will be provided for median time to event.

Proprietary confidential information © 2018 Boehringer Ingelheim International GmbH or one or more of its affiliated companies

Objective response

The binary endpoint OR will be analysed in an exploratory manner.

Moreover, logistic regression will be used to test for a difference between the two arms for objective response rate. The model will be adjusted for the stratification factor visceral involvement by fitting this as an explanatory variable. The exploratory p-value will be generated from the likelihood ratio test statistic. An odds ratio and corresponding 95% CI will be generated using the likelihood ratio CI in order to obtain a direct correspondence between the p-value and the odds ratio CI. Odds ratios >1 favour xentuzumab + everolimus + exemestane.

Disease control

DC will be analysed similarly to OR, see above.

Time to OR

Descriptive statistics will be calculated for time to OR. This will only be computed for patients who have an OR.

Duration of OR

Duration of OR will be assessed based on the Kaplan-Meier method for each treatment arm separately. Point estimates together with CIs (based on Greenwood's method) will be provided for median time to event and quartiles. This will only be computed for patients who have an OR.

[figure not shown]
Duration of DC

Duration of DC will be analysed similarly to Duration of OR, see above.

Proprietary confidential information © 2018 Boehringer Ingelheim International GmbH or one or more of its affiliated companies

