Death without progression, but two or more consecutively missed radiological assessments prior to death	Censored	Date of last radiological assessment prior to missed assessments
Initiation of subsequent anti-cancer therapy		
Subsequent anti-cancer therapy started before progression or death, no more than one consecutively missed radiological assessments prior to start of subsequent anti-cancer therapy	Censored	Date of last radiological assessment before initiation of subsequent anti-cancer therapy

Proprietary confidential information © 2018 Boehringer Ingelheim International GmbH or one or more of its affiliated companies

Only radiological assessments after first assessment indicating objective response will be taken into consideration.

Disease control (DC)

DC is defined as best overall response of CR or PR, or SD \geq 24 weeks, or Non-CR/Non-PD for \geq 24 weeks where best overall response is defined according to RECIST version 1.1 from date of randomisation until the earliest of disease progression, death or last evaluable tumour assessment before start of subsequent anti-cancer therapy (see [Section 5.4.7](#)).

Duration of DC

Duration of DC is defined as the time from randomisation until the earliest of disease progression or death, among patients with DC.

Duration of DC will only be calculated for patients with a DC. For patients with disease progression or death:

- Duration of DC [days] = date of outcome – date of randomisation + 1.

For patients without disease progression or death:

- Duration of DC (censored) [days] = date of outcome – date of randomisation + 1.

The censoring rules for duration of DC are given in Table 5.2.2.2: 3.

[figure not shown]
Table 5.2.2.2: 3 Derivation rules for Duration of Disease Control

[figure not shown]
Situation	Outcome (event or censored)	Date of outcome
With baseline and post-baseline radiological assessments BUT no other anti-cancer therapy		
Alive and not progressed, no more than one consecutively missed radiological assessments	Censored	Date of last radiological assessment
Alive and not progressed, two or more consecutively missed radiological assessments	Censored	Date of last radiological assessment prior to missed radiological assessments
Progressed, zero or one missed radiological assessment prior to progression	Event	Date of radiological assessment of progression

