7 PLANNED ANALYSES

The labelling and display format of statistical parameters will follow BI standards [\(7\)](#).

Unless otherwise specified, outputs will be displayed separately for each part of the trial.

Descriptive statistics for continuous variables will generally contain N (number of patients in that patient set with non-missing values), Mean, Standard Deviation, Minimum (Min), 25th percentile (Q1), Median, 75th percentile (Q3), Maximum (Max). In general, means, standard deviations, medians, Q1 and Q3 will be presented to one more decimal place than the raw data. Minima and maxima will be presented to the same number of decimal places as the raw data.

For time-to-event analysis tables, the set of statistics is: number of patients [N (%)], Number of patients with event [N (%)], Number of patients censored [N (%)], <Time to event> [months] followed by Q1 (25th percentile), Median, Q3 (75th percentile). If not specified otherwise, the duration as well as time to event will be displayed in months.

Tabulations of frequencies for categorical data will include all possible categories and will display the number of observations in a category as well as the percentage (%) relative to the respective treatment group total. Percentages will be rounded to one decimal place.

In general a category “missing” will be displayed, if there are missing data for the corresponding variable. Percentages will also generally be based on all patients in the respective patient set whether they have non-missing values or not.

The primary analysis will include all treated (Phase Ib) or randomised patients (Phase II), following the ITT approach (as specified in [Section 6.3](#)).

The analyses for the primary endpoint of PFS as well as best overall response, OR, time to OR, duration of OR, DC, duration of DC, time to progression, tumor shrinkage, tumor size as well as the [REDACTED] will be based on data obtained until November 25th 2016. A sensitivity analysis for the primary endpoints PFS will be performed using all data. Analyses of other RECIST based endpoints will also only utilise data obtained from assessments scheduled until November 25th 2016. For overall survival all available data will be used.

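### On the SAP text available, a stable patient randomised too late to reach week 24 by 25 November 2016 cannot count as disease control but stays in the denominator

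*SAP*

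**What the plan says.** **Definition.** SAP 5.2.2.2: "DC is defined as best overall response of CR or PR", or SD or Non-CR/Non-PD lasting at least 24 weeks. For best overall response it refers to SAP 5.4.7.

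**Cut-off.** SAP 7 lists the endpoints concerned, among them "best overall response, OR, time to OR, duration of OR, DC, duration of DC, time to progression", and says the analyses "will be based on data obtained until November 25th 2016". SAP 7.5.2.2 repeats that "only response assessments until the cut-off date of 25th November 2016 will be used for the analysis of all response-based endpoints".

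**Set and denominator.** SAP 7.5.2.2: "Secondary endpoints will be analysed descriptively for all patients in the randomised set in the second part of this trial". SAP 7: "Percentages will also generally be based on all patients in the respective patient set whether they have non-missing values or not".

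**Method.** "DC will be analysed similarly to OR, see above". For OR this means a logistic regression adjusted for visceral involvement, with no term for length of follow-up.

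**Recruitment.** SAP 4.2 dates the sponsor's decision to stop recruitment, and xentuzumab, to 28 October 2016.

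**What PFS gets.** SAP 7.4.2 censors patients ongoing at the cut-off at their last assessment. SAP 7 adds: "A sensitivity analysis for the primary endpoints PFS will be performed using all data". The supplied text has no counterpart for DC. Duration of DC uses Kaplan-Meier, but only in patients already counted as DC.

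**The concern.** A 24-week criterion scored as yes or no needs 24 weeks of potential follow-up in everyone who is scored. The planned design gave that with room to spare; the early cut-off may not. A patient with early CR/PR, or with early progression, is still scored correctly. A patient who is stable and simply recent is scored as a failure, so short follow-up is read as lack of disease control.

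The analysis is exploratory. However, protocol 7.2 bases inference on the size of the observed differences in PFS and other efficacy endpoints, and SAP 4.2 says the report is to document the trial for future ones. A DC rate that reads too low could mislead anyone who compares it with another trial.

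**Working it through.** **1. The plan's own figures.** Protocol 7.6 assumes 12 months of accrual, exponential PFS with medians 10.8 and 7.8 months, and 90 events. Solving 150 × (1 − c) × F(T) = 90, with the protocol's formula for F and c = 20%, 25%, 30% permanently censored, gives T = 24.90, 27.93 and 32.54 months. The protocol states 24.9, 27.9 and 32.5. The shortest potential follow-up would have been 24.9 − 12 = 12.9 months, so the DC definition did no harm as planned.

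The SAP 6.7.2 rule also reproduces: week 24 is due on day 24 × 7 + 1 = 169. The window runs from (113 + 169)/2 + 1 = 142 to (169 + 225)/2 = 197, with Day 1 the randomisation date.

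**2. Last randomisation dates that allow a week-24 success by 25 November 2016.**

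| Reading of 24 weeks | Days after randomisation | Last date |
|---|---|---|
| Full 168 days | 168 | 10 June 2016 |
| Start of the protocol's week-24 scan slot (Phase II flow chart, footnote 15) | 161 | 17 June 2016 |
| Start of the SAP window, day 142 | 141 | 7 July 2016 |

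From 28 October to 25 November is 28 days, the potential follow-up of a patient randomised on the day recruitment stopped. The choice of reading moves the date by at most 27 days and does not remove the problem.

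**3. Direction.** Let S be the true 24-week control rate in an arm, f the share randomised too late, and r the share of those already credited through CR/PR. The observed rate is (1 − f) × S + f × r. It is below S whenever f > 0 and r < S. Randomisation makes f about equal in the two arms, so with no true effect the odds ratio stays at 1.

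**4. Illustration only.** Assumptions: planning medians, 168-day reading, no dropout, r = 0. 168 days = 168 × 12/365.25 = 5.52 months. Control S = exp(−0.0889 × 5.52) = 61.2%; triplet S = exp(−0.0642 × 5.52) = 70.2%.

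| f | Control | Triplet | Difference (points) | Odds ratio |
|---|---|---|---|---|
| 0 | 61.2% | 70.2% | 8.9 | 1.49 |
| 10% | 55.1% | 63.2% | 8.0 | 1.40 |
| 20% | 49.0% | 56.1% | 7.2 | 1.33 |
| 30% | 42.9% | 49.1% | 6.3 | 1.29 |
| 38% | 37.8% | 43.3% | 5.5 | 1.26 |

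The rate ratio stays at 70.2/61.2 = 1.15. Each 10% affected costs 6.1 to 7.0 points. With r = 12.6%, the everolimus-exemestane response rate quoted in protocol 1.1, it costs 0.1 × (61.2 − 12.6) = 4.9 to 0.1 × (70.2 − 12.6) = 5.8 points.

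**5. What f might be.** The documents do not say. Three assumed uniform 12-month accruals show the spread:
- From 11 June 2015, the date of the first TSAP version, which was signed before the safety snapshot used to set the Phase II dose: accrual ends by 10 June 2016 and f = 0.
- From 4 August 2015, the date of the interim report: 54 of 365 days fall after 10 June 2016, so f is about 15%. The loss is 9 to 10 points with r = 0.
- Ending 28 October 2016 at the planned 12.5 per month: 140 days = 4.60 months, 57 of 150 patients, f = 38%. The loss is 23 to 27 points.

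**The case against.** **The deciding rule may sit in text not supplied.** SAP 5.2.2.2 points to 5.4.7, and SAP 4.2 says the SAP follows protocol amendment 3; neither is in the supplied text. This stands. A reader might infer that no follow-up-adjusted DC analysis is planned anywhere, and the documents do not support that. Even so, a scan tolerance or a minimum SD duration in 5.4.7 would only move the dates in step 2. Only a rule about potential follow-up would remove the problem, and the DC analysis in 7.5.2.2 shows none.

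**The size is unknown.** This also stands. Step 4 ignores the 20–30% permanently censored patients of protocol 7.6. If all of them left before week 24 and counted as failures (an extreme case), the 6.1 points per 10% would fall to 6.1 × 0.8 = 4.9 or 6.1 × 0.7 = 4.3.

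**Scoring unconfirmed control as failure is a conservative convention, nothing is formally tested, and PFS and TTP handle short follow-up by censoring.** All true, and this limits the severity. But PFS and TTP are different endpoints, as are the PFS rates at, for example, 2, 4 and 6 months in protocol 7.3.1. A descriptive DC rate is meant to describe, so an understated one matters a little. The all-data PFS repeat does not imply a need for an all-data DC analysis: later scans follow the end of xentuzumab.

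**A simple 168-day subset would not always work.** Correct. On-time week-24 scans fall at days 161–168. If a literal 168 days is required, a scan at day 161 to 167 is too early and confirmation waits for days 217–224. The subset limit must follow the DC derivation.

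**Conclusion.** The point holds on the SAP text available, subject to SAP 5.4.7 and amendment 3. If any stable non-responders were randomised too late for the qualifying week-24 assessment, the absolute DC rate is biased low in both arms and a true odds ratio is pulled towards 1.

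Two stronger readings are tempting. One is that the comparison favours an arm or creates a false difference. It does not: the shortfall falls on both arms about equally, and with no true effect the odds ratio stays at 1. The other is that the DC rate is too low by some stated amount, because recruitment was stopped so near the cut-off. The documents give neither randomisation dates nor the number randomised, so the loss may be zero. Every figure in steps 4 and 5 illustrates assumed accrual, planning medians and no dropout.

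Severity: minor. Label: cheap improvement.

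**What to change.** First check SAP 5.4.7 and amendment 3 for how ongoing stable disease of less than 24 weeks at the cut-off is classed, and which scan confirms 24 weeks.

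Keep the all-randomised DC analysis. Add to SAP 7.5.2.2 a supportive analysis (DC rates per arm and the same logistic model) in patients randomised early enough that the assessment able to confirm 24-week control fell due on or before 25 November 2016:
- protocol slot qualifies: end of slot, 168 days, randomised by 10 June 2016;
- SAP window qualifies: end of window, day 197 = 196 days after randomisation, by 13 May 2016;
- literal 168 days required: end of the next slot, 224 days, by 15 April 2016.

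Randomisation date is fixed before treatment, so the subset keeps the randomised comparison. Report per arm how many patients had less potential follow-up, and interpret the absolute DC rate from the subset. Note that some patients in it had xentuzumab stopped by the sponsor on 28 October 2016 before week 24. Since 28 October − 168 days = 13 May, this concerns those randomised from 14 May to 10 June under the first limit.

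Cost: one paragraph and one flag, no new data. The downside is a smaller subset and a wider interval. If 75 per arm were randomised uniformly over 12 months to 28 October 2016, the limits leave about 46, 40 or 35 per arm. With rates 0.70 and 0.61, the standard error of the difference, √[(0.210 + 0.238)/n], rises from 7.7 points at n = 75 to 9.9, 10.6 or 11.3.

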7.7 EXTENT OF EXPOSURE

The variables defined in [Section 5.4.2](#) will be summarised descriptively for each dose cohort (Phase Ib) or treatment group (Phase II).

For the phase II part, this variables will also be provided by visceral involvement.

7.8 SAFETY ANALYSES

All safety analyses will be performed on the TS (unless otherwise specified; for example, the MTD Set will be used for some safety outputs). Patients in the Phase Ib part of the trial who were replaced within or before the first treatment cycle will be excluded from the determination of the MTD.

7.8.1 Adverse events

The analyses of AEs will be descriptive in nature. All analyses will be based on the number of patients with AEs (not the number of AEs).

Proprietary confidential information © 2018 Boehringer Ingelheim International GmbH or one or more of its affiliated companies

For analysis multiple AE occurrence data on the CRF will be collapsed into an AE event provided that all of the following applies:

- All AE attributes are identical (Lowest Level Term (LLT), Common Terminology Criteria for Adverse Events (CTCAE) grade, action taken with trial medication, therapy required, seriousness, reason for seriousness, relationship, outcome, AE of special interest)
- The occurrences were time-overlapping or time-adjacent (time-adjacency of 2 occurrences is given if the second occurrence started on the same day or on the day after the end of the first occurrence)

For further details on summarisation of AE data, please refer to [\(2\)](#) and [\(4\)](#).

Adverse events will be coded with the most recent version of MedDRA. The severity of AEs will be scaled according to CTCAE (CTCAE version 4.03 ([R10-4848](#))).

The analyses of AEs will be based on the concept of treatment-emergent AEs. For the phase Ib, that means that all AEs with an onset between first treatment administration until end of the REP will be assigned as 'on treatment'. All adverse events occurring before first drug intake will be assigned to 'screening' and all adverse events occurring after the REP will be assigned to 'post-treatment'; these AEs will be displayed in separate tables and listings. First drug intake includes the run-in period for Phase Ib part.

For the phase II part it has to be taken into consideration that the sponsor decided to stop treatment with xentuzumab on 28th of October 2016, but continued treatment with everolimus and exemestane. Therefore, the analysis of on-treatment AEs will be split in two parts:

1) AEs with onset date on or before 9th of December 2016

This includes the following patients:

- Patients of both arms who completed the REP on or before 9th of December 2016, i.e. AEs until the end of REP will be considered.
- Patients who stopped xentuzumab on 28th of October 2016 due to sponsor's decision, i.e. AEs with onset date on or before the 9th of December 2016 will be considered.
- Patients receiving everolimus and exemestane only, i.e. AEs with onset date on or before 9th of December 2016 will be considered.

2) AEs with onset after 9th of December 2016

This includes the following patients:

- Patients who stopped xentuzumab on 28th of October 2016 due to sponsor's decision, i.e. AEs with onset date after 9th of December 2016 will be considered.
- Patients receiving everolimus and exemestane only, i.e. AEs with onset date after 9th of December 2016 will be considered.

Both parts will be analyzed by treatment and a total column will be given.

Proprietary confidential information © 2018 Boehringer Ingelheim International GmbH or one or more of its affiliated companies

For the Phase II part all AEs occurring before first drug intake will be assigned to 'screening' and all AEs occurring after the REP will be assigned as 'post-treatment'.

AEs will be displayed by the initial dose of study medication administered on the first day of treatment (or planned to be administered, for the run-in period of the Phase Ib part).

An overall summary of AEs will be presented. The frequency of patients with AEs will be summarised by treatment, primary system organ class (SOC) and preferred term (PT).

Separate tables will be provided for patients with drug-related AEs, AEs leading to dose reduction, AEs leading to discontinuation, serious adverse events (SAE), serious drug-related AEs, AEs leading to death, other significant AEs, adverse events of special interest (AESI), and AEs fulfilling the DLT definition (for phase Ib part only). For the Phase II part an overall summary of AEs as well as a table for AEs and SAEs by treatment will be provided for the subgroups of visceral involvement.

Sorting order:

In tables presenting SOC and PT, SOCs will be sorted alphabetically and PTs (within SOC) by descending frequency.

Reporting of CTCAE grades in tables:

In tables showing AEs by worst CTCAE grade, AEs with missing CTCAE grade will only be displayed under the category "All grades", but no category "Missing grade" will be displayed. Therefore the categories "Grade 1" to "Grade 5" might not add up to the category "All grades"; a footnote will explain this handling.

Displaying of CTCAE grades in AE tables (Section 15) will be "All grades", "Grade 1", "Grade 2", "Grade 3", "Grade 4", and "Grade 5" separately. In the appendix (Section 16.1.9.2), the categorisation "All grades", "Grade 1/2", "Grade 3/4/5", will be used.

Listings of AEs

AEs will be reported with start and end day as calculated from the first day of treatment with study medication. This includes the run-in period for the Phase Ib part.

Incidence and severity of AEs

The incidence of AEs overall (irrespective of relatedness to study medication), related AEs, and SAEs will be reported by severity according to CTCAE grades.

Other significant AEs

Other significant AEs are defined as serious and non-serious AEs that lead to dose reduction or permanent discontinuation of study medication. Their incidence will be reported by severity according to CTCAE grades.

A listing of patients who developed 'other significant' AEs will be provided and a flag for serious and non-serious will be included.

AEs leading to dose reduction or permanent discontinuation will include:

- AEs leading to dose reduction of xentuzumab
- AEs leading to dose reduction of everolimus

Proprietary confidential information © 2018 Boehringer Ingelheim International GmbH or one or more of its affiliated companies

- AEs leading to permanent discontinuation of xentuzumab
- AEs leading to permanent discontinuation of everolimus
- AEs leading to permanent discontinuation of exemestane

AEs leading to death

AEs leading to death during the on-treatment period will be tabulated in a separate table. In this table no CTCAE grades will be shown. For fatal AEs without CTCAE grade 5 or missing grade, the grade will be imputed as CTCAE grade 5. Reported fatal AEs that occurred in the post-treatment period will be listed within the listing containing all post-treatment AEs.

Protocol-specified AESIs

Protocol-specified AESIs are specified in the CTP Section 5.2.2.1. Their incidence will also be reported. DLTs are considered as AESIs only in the Phase Ib part.

Adverse events by user defined AE categories (UDAEC)

UDAEC as defined on project level by the pharmacovigilance working group will be derived and the latest version will be used for the analysis. The categories will be taken as defined in the most recent signed version of the safety Statistical Analysis Plan (SAP) at the time of the DBL. These categories can be found in Table 7.8.1: 1. This document is entitled "8-02-sap-safety-core", which can be found in the Project Data Management and Statistics folder, section 8 (project level), within BIRDS.

Table 7.8.1: 1 Adverse events by user defined AE categories

Term	Group[#]
Hepatic impairment	Drug related hepatic disorders – comprehensive search (SMQ)
Hyperglycaemia narrow	Hyperglycaemia/new onset diabetes mellitus (SMQ) – narrow
Infusion related reaction	IRR (BIcMQ) Hypersensitivity (SMQ) – narrow
Non-infectious pneumonitis	Interstitial lung disease (SMQ) – narrow
Renal insufficiency	Acute renal failure (SMQ) – broad
Weight loss	Weight loss (BIcMQ) – broad
Neutropenia	Haematopoietic leukopenia (SMQ) – narrow
Stomatitis	Stomatitis (BIcMQ) – broad
Asthenia	Asthenic conditions (BIcMQ) – narrow
Anemia	Haematopoietic erythropenia (SMQ) – broad
Thrombocytopenia	Haematopoietic thrombocytopenia (SMQ) – narrow

[#] This column indicates whether the Term(s) provided in the first column are MedDRA preferred terms (**PT**), Standardised MedDRA Queries (**SMQ**) or BI customised MedDRA Queries (**BIcMQ**).

The incidence of AE by UDAEC will be analysed.

Proprietary confidential information © 2018 Boehringer Ingelheim International GmbH or one or more of its affiliated companies

